8.2 Exclusion criteria

- 1) Any study ulcer of the NPUAP Stage I, II or IV
- 2) Diabetic ulcer or Venous ulcer (or stasis ulcer)
- 3) Past history of surgical treatment within 1 year or irradiation at the target pressure ulcer within 1 year
- 4) Hypersensitivity reaction to this product or povidone-iodine
- 5) Hyperthyroidism or thyroid disorder requiring drug treatment
- 6) Signs of a current underlying systemic infection (sepsis/bacterial infection/tuberculosis) or cellulitis or osteomyelitis
- 7) Type 1 diabetes
- 8) Current malnutrition
- 9) Heavy smoker: Current smoking level of ≥ 1 pack (20 cigarettes)/day of tobacco
- 10) Drug or alcohol addiction
- 11) Requirement of immunosuppressants during the study or current chemotherapy or radiotherapy
- 12) Application of other investigational product/medical device within 1 month prior to the

investigational device application (1d)

13) Pregnant or breastfeeding women

14) Other renal, hepatic, neurological, immunological disorder that may interfere with the wound healing process, at the discretion of the investigator

9. Target number of subjects and the rationale

The target number of subject enrollment is 20 subjects, with 10 subjects per group.

This study has a purely explorative goal so that no formal sample size calculation will be conducted but it was planned to enroll 10 subjects per group as the minimum sample size to achieve study objectives from a scientific perspective.

- ✓ Medifoam group: 10 subjects
- ✓ Betafoam group: 10 subjects

Even if a subject is withdrawn from the study, the subject will not be replaced.

10. Study method

10.1 Study design

[figure not shown]
This is a single-center, randomized, 2-arms, open-label pilot study.

Subjects who consent to the study will be assessed for eligibility with screening tests. Subjects can have a 2-week screening period.

After screening, subjects who meet the inclusion/exclusion criteria will apply Medifoam[®] or Betafoam[®] for 12 weeks, after randomization. Targeted subjects are outpatient clinic or hospitalized patients. Subjects will make once weekly site visits.

During the treatment period, dressing is performed twice weekly, but additional dressing changes are allowed, depending on the condition of the pressure ulcer, such as excessive exudates at the study ulcer. Nevertheless, the frequency of additional dressing is limited to twice per day. On the weekly site visit days, the investigator (or clinical research coordinator) will change the dressing; on other occasions, the subject or guardian will perform self-dressing. Subjects who achieve complete healing of the target pressure ulcer within 12 weeks will have early completion.

Efficacy assessment is conducted for a total of 12 times at a 1-week interval, after the investigational device application (8d, 15d, 22d, 29d, 36d, 43d, 50d, 57d, 64d, 71d, 78d, 85d). At each efficacy assessment, the investigator (or clinical research coordinator) should take a digital photograph of the target pressure ulcer and retain it as a source document.

10.2 Investigational device application methods

[Investigational devices]

Medifoam[®] (Mundipharma)

Betafoam[®] (Mundipharma)

[General investigational device application method]

An appropriate type of the investigational device should be selected for the study ulcer size and it should be able to completely cover the target pressure ulcer. At every dressing change, record the selected investigational device size in the source document.

[Investigational device application sequence]

- ① Carefully wash the target pressure ulcer with normal saline.
- ② After washing, wipe the study ulcer for drying with sterilized gauze, if necessary. At this time, pay attention not to irritate the study ulcer.
- ③ Select a study device that is larger than the pressure ulcer, open the product packaging, take out the device using tweezers, and remove the release film. Directly cover the wound with the foam side without the release film, paying attention to completely cover the wound.
- ④ If necessary, fix around the edge of this product with surgical tape or Band-Aid while paying attention not to attach too tight to avoid skin irritation.
- ⑤ If there is a lot of exudate and a leak is likely to occur at the study ulcer, exchange the dressing more frequently than planned (twice weekly).

[Application frequency]

- Twice weekly

During the 12-week treatment period, dressing is performed twice weekly, but additional dressing changes are allowed, depending on the condition of the pressure ulcer, such as excessive exudates at the lesion. Nevertheless, the frequency of additional dressing is limited to twice per day. In case of additional dressing changes beyond twice weekly changes, the change frequency should be recorded in the Case Report Form.

On the weekly site visit days, the investigator (or clinical research coordinator) will change the dressing; on other occasions, the subject or guardian will perform self-dressing. The investigator (or clinical research coordinator) will train the subject or guardian on the dressing method at every visit.

10.3 Subject enrollment method

As this study will enroll 10 subjects per group without using a control group through randomization. Note that it was planned to enroll 10 subjects per group as follows, as the minimal sample size to achieve study objectives from a scientific perspective.

	Group A	Group B
Study device	Medifoam [®]	Betafoam [®]

Subjects will be enrolled to a Medifoam group and a Betafoam group by randomization to reduce the possible bias which may be caused by the investigator, and once 10 subjects are enrolled in each group, no further enrollment will take place. In addition, even though a subject is withdrawn during the study, the subject will not be replaced.

Clinical Research team of this trial will request to create Randomization List to independent statistician (person in charge of randomization) who is not involving in this study. Randomization list contains the information of subjects assigned upon randomization code. A person in charge for randomization will create and operate Randomization list independently.

Randomization will be generated by randomization program of SAS system. And the permutation of random numbers (random number of A and B) will start from number 1 in consecutive order (i.e. A: Group A, B: Group B). Block size won't be stated in this protocol.

The site will assign the following number to subjects in the order of signing the Informed Consent Form.

Screening Number SXY (X: Site number/A, Y: Serial Number in two digits / 01, 02, 03~)
(i.e. : SA01, SA02, SA03, SA04,...)

Investigator will grant assigned number to the appropriate subject who is eligible for inclusion/exclusion criteria in consecutive order, and the subject will go through randomization. And proper investigation device will be applied to the subject upon assigned group.

Assigned Number RXY (X: Site number/A ; Y: Serial Number in two digits / 01, 02, 03~)
(i.e. : RA01, RA02, RA03, RA04,...)

10.4 Concomitant therapy and standard treatment

During the study, the following drugs are prohibited from concurrent use. In addition, in case a drug/medical device used for treatment without being determined by the principal investigator is expected to possibly affect the efficacy assessment of this study, the relevant subject may be excluded from efficacy analysis during result analysis. The final efficacy set will be determined in a blinded

meeting.

<Prohibited concomitant medication>

- ✓ Any external use preparation for pressure ulcer treatment (however, povidone-iodine may be allowed, if necessary.)
- ✓ Local antibiotics applied to the target pressure ulcer: However, in case of inevitable treatment, it can be applied. Other than local antibiotics, systemic antibiotics including injectable or oral preparations are allowed.
- ✓ Immunosuppressants
- ✓ Glucocorticoids. However, they may be administered when necessary, at the discretion of the investigator.

<Standardization of pressure ulcer care>

- ✓ Position change: The investigator (or coordinator) will instruct the subject or guardian on the daily position changes. A subject who stays sitting or lying only should be instructed to change the position once every 2 hours.

11. Study period

24 months from the protocol approval date by the Institutional Review Board

12. Observation and test items

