15.1 General principles of result analysis

Data obtained from subjects in this study will be analyzed as the SS(Safety Set) and the FAS(Full Analysis set).

- 1) In the SS(Safety set), data obtained from subjects who were enrolled in the study, had at least

- 1 application of the study device, and had at least 1 safety assessment will be analyzed.
- 2) In the FAS(Full analysis set), data obtained from subjects who were enrolled in the study, had at least 1 application of the study device and then had at least 1 available endpoints of main interest review will be included in analysis.

Efficacy and demographics will be analyzed using the FAS and safety data will be analyzed using the SS.

For subjects with a missing value during the study or who are withdrawn from the study prior to study completion, efficacy analysis will be conducted by applying the LOCF (Last Observation Carried Forward), only in case such subjects have available endpoints of main interest assessment results after the investigational device application. However, in case of missing values for Other endpoints and safety endpoints, raw data will be used for analysis, without applying LOCF.

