Plans to include informed consent from legally acceptable representatives

If it is not possible to obtain informed consent from the subject due to lack of his/her abilities to understand and express opinions, informed consent will be obtained from the subject's legally acceptable representative (person with parental rights, spouse, or guardian). In this case, the investigator should confirm that this individual is a legally acceptable representative of the subject through a document proving this fact and should record in the subject information sheet and the source document the reason the informed consent was obtained from the legally acceptable representative.

The investigator should also confirm that vulnerable subjects were given sufficient information about the study and voluntarily provided informed consent.

22. Compliance with the study and handling of protocol deviations

The principal investigator and sub-investigators of this study should remain fully aware of and thoroughly implement the protocol to prevent any protocol deviation. In this study, training will be given for application of the investigational devices to subjects as scheduled, and the investigator should take appropriate measures so that subjects would not miss but make outpatient visits on scheduled dates to ensure compliance with the study schedule.

Meanwhile, unavoidable protocol deviations will be handled as follows:

- In case of a serious deviation, the subject may be excluded from the efficacy set during the efficacy assessment of the study.
- For minor deviations, the extent of the deviation or delay and the reason will be accurately recorded, and it will be considered whether they influenced the study results during result analysis. The final efficacy set will be determined in a data review meeting.

23. Publication policy**23.1 Ownership**

Mundipharma Pte Ltd has the right to all data generated from this study and all data that is provided to Mundipharma Pte Ltd.

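### Protocol 10.4 and 22 allow judgement-based removal of subjects from the efficacy analysis, on grounds that the full analysis set definition does not contain

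*Protocol*

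**What the plan says.** **Analysis set.** Protocol 15.1 states: "Efficacy and demographics will be analyzed using the FAS and safety data will be analyzed using the SS". Protocol 15.1 and SAP 6 define the FAS by two facts, one application of the device and one available review of a main endpoint. Protocol 15.1 and SAP 9 also keep withdrawn subjects who have such a review, by last observation carried forward (LOCF). Neither document defines a per-protocol set.

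**Exclusions.** Protocol 10.4 covers the case where "a drug/medical device used for treatment without being determined by the principal investigator is expected to possibly affect the efficacy assessment". In that case, "the relevant subject may be excluded from efficacy analysis during result analysis". Protocol 22 adds: "In case of a serious deviation, the subject may be excluded from the efficacy set during the efficacy assessment of the study".

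**Who decides.** Protocol 10.4: "The final efficacy set will be determined in a blinded" meeting. Protocol 22: "The final efficacy set will be determined in a data review meeting". Protocol 10.1 describes the design: "This is a single-center, randomized, 2-arms, open-label pilot study".

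**Sub-analyses.** Protocol 15.3 asks for efficacy sub-analyses by use of local antibiotics and glucocorticoids during the study, and names no test. Protocol 16.2 says that no formal statistical test will be done. SAP 8 item 5 adds a between-arm t-test and a paired within-arm t-test. Tables 0605 and 0606 carry a between-arm p-value at each visit for users and for non-users. Use depends on events after randomisation. Protocol 10.4 lists among the prohibited treatments: "Local antibiotics applied to the target pressure ulcer: However, in case of inevitable treatment, it can be applied".

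**The concern.** The FAS is set by facts that leave no room for choice, and it keeps even subjects who withdraw after one review. The two exclusion rules work the other way. They are permissive, rest on judgement, and are applied while results are being analysed or efficacy assessed, when outcomes and arm may be known. If removal is related to how the ulcer is doing, the arms are no longer compared as randomised. Protocol 9 does not replace withdrawn subjects, and nothing provides for making up an exclusion.

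The study is exploratory, but Protocol 5.1 says that a further trial will use its result, so the healing estimates matter even without a confirmatory claim.

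The secondary issue is that a p-value within users or non-users of a drug started during the study can be read as a device effect. It may come from a handful of subjects, sorted by something that happened after allocation.

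**Working it through.** The plan gives no healing rate, usage rate or power figure, so there is no stated number to reproduce. The rates below are assumptions, shown over a range.

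**1. Do the exclusion grounds appear in the FAS definition?**
- Protocol 10.4: a treatment not determined by the principal investigator that might affect efficacy. This is a trigger, but a judgemental one, with no list, duration or timing. It is not in Protocol 15.1 or SAP 6.
- Protocol 22: a serious deviation, with no definition. It is not in Protocol 15.1 or SAP 6.
- SAP Table 0103 has open rows for reasons for FAS exclusion and does not say what may go in them.

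**2. Effect of an exclusion on the healing difference.** Inputs: 10 per arm (Protocol 9), all assumed to be in the FAS; equal healing of h out of 10 in both arms (assumed, h = 2 to 7); k subjects dropped from one arm.
- Non-healers dropped: h/(10−k) − h/10, which is h/90 for k = 1 and h/40 for k = 2.
- Healers dropped: (h−k)/(10−k) − h/10, which is (h−10)/90 for k = 1 and (h−10)/40 for k = 2.

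Difference created, in percentage points:

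| h | 1 non-healer | 2 non-healers | 1 healer | 2 healers |
|---|---|---|---|---|
| 2 | +2.2 | +5.0 | −8.9 | −20.0 |
| 5 | +5.6 | +12.5 | −5.6 | −12.5 |
| 7 | +7.8 | +17.5 | −3.3 | −7.5 |

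**3. If exclusion is unrelated to healing.** For k = 1 the mean shift is (h/10)(h−10)/90 + ((10−h)/10)(h/90) = 0. With p = h/10, the standard deviation is √(p(1−p))/9 for k = 1, or 4.4 to 5.6 points, and √(p(1−p))/6 for k = 2, or 6.7 to 8.3 points. So unrelated exclusions add noise but no bias.

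**4. Stratum tests.** There are 2 drugs × 2 levels (used, not used) × 12 post-baseline visits = 48 between-arm p-values, if every stratum has enough subjects.

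A t-test using both arms' spread needs at least two subjects in each. If a fraction u of subjects uses the drug, independently, the chance that at least one arm has fewer than two users is 1 − (1 − B)², with B = (1−u)¹⁰ + 10u(1−u)⁹. At u = 0.2, B = 0.107 + 0.268 = 0.376, and 1 − 0.624² = 0.61. At u = 0.3, 0.4 and 0.5 the result is 0.28, 0.09 and 0.02.

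**The case against.** **The set may already be fixed.** SAP 6 names only the safety set and the FAS, and it repeats no discretionary exclusion. The Table 0103 rows match the safety-set rows above them and most naturally mean failure of the definition. The final efficacy set could simply be the FAS after review. This is a fair reading, but SAP 11 says that the analysis follows the protocol in principle, and the protocol still contains both exclusion rules. The passages have to be reconciled.

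**The decision is not left to one person.** A reader might infer that there is no criterion at all, or that each analyst may choose a set. The documents do not support that: 10.4 gives a trigger, and both sections assign the decision to a meeting, possibly the same one. A masked meeting would be a partial safeguard. It would not supply the missing criterion, and no text describes the masking.

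**Exclusions could make a result significant.** A reader might infer this, but no significance level is set for the between-arm tests and Protocol 16.2 plans no formal test, so there is no threshold to cross. The effect is on the estimate.

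**All local antibiotic users could be dropped.** The text does not support this. The exclusion clause is stated in addition to the listed drugs, 10.4 permits local antibiotics where treatment is inevitable, and 15.3 requires users to be analysed. Only a local antibiotic not determined by the principal investigator is ambiguous: it could lead to removal under 10.4 or to a place among the users in Table 0605.

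**The stratum comparisons must be seriously biased.** That would need use to depend on both arm and prognosis, and the documents give no usage rates. The firm objections are small numbers, loss of the randomised comparison, and conflict with 16.2.

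**Conclusion.** The point holds for the exclusion wording. Protocol 10.4 and 22 allow removal after randomisation, on judgement or for an undefined deviation, from a set that Protocol 15.1 and SAP 6 define by fact. Each removal is 10% of an arm. One outcome-related removal shifts the healing difference by about 2 to 9 percentage points in either direction, and two shift it by 5 to 20, on the assumption of equal healing between 2/10 and 7/10. These are consequences if removal is related to outcome, not a forecast that it will be.

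The stratum p-values are a secondary matter of presentation. They exceed what Protocol 15.3 asks for and sit badly with 16.2. At an assumed 20% use, the user comparison fails to have two subjects in each arm 61% of the time. The unstratified results in Tables 0601, 0603 and 0604 are not touched by this second point.

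A reader might add Table 0602, which tests healing time among healers only. That belongs with the Kaplan-Meier handling of non-healers and is not part of this point.

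**What to change.** - Delete the exclusion wording in Protocol 10.4 and 22, so that every efficacy analysis uses the FAS by randomised arm. Alternatively, confine it to a labelled supplementary per-protocol analysis, with criteria listed in the SAP and fixed before database lock, decided in one named meeting whose masking is described.
- Limit the FAS-exclusion reasons in Table 0103 to failure of the SAP 6 definition.
- Remove the between-arm t-test from SAP 8 item 5 and the p-value column from Tables 0605 and 0606. Keep the descriptive sub-analyses that Protocol 15.3 requires, with the number of users per arm and a footnote that the strata were formed after randomisation.
- The paired within-arm test stands in the same SAP sentence but has no row in Tables 0605 or 0606. State openly whether it is kept, so that it is not lost as a side effect of the edit.

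The cost is wording in two protocol sections and the SAP, and two simpler tables. No new data are needed, because concomitant treatment is already reviewed at every scheduled visit. A supplementary per-protocol analysis, if wanted, adds a short list of criteria.

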12.1 Schedule of study activities

12.1.1 Visit 1 (screening, -14d~0d)

Written Informed Consent Form should be first obtained from subjects prior to any test. Tests to be conducted at screening are as follows, and in case all tests are completed and test findings can be confirmed on the day of screening, Visit 1 and Visit 2 can be take place together. If Visit 1 and Visit 2 are taken place on the same day, duplicated tests (Physical Examination, Inclusion/Exclusion criteria, , Concomitant medication/treatment review) are only done once.

- ① Before involving a subject in the study, the subject will be informed of the study process and then the subject (or representative) will provide informed consent.
- ② Subject numbers will be assigned in the order of completing the Informed Consent Form.
- ③ Collect demographic information and medical history.
- ④ Conduct the physical examination.
- ⑤ As vital signs, measure blood pressure, pulse, and body temperature.
- ⑥ Conduct laboratory tests (hematology, blood chemistry). If test findings within 2 weeks prior to the consent date are available, they can be used instead.
- ⑦ Measure height and body weight of the subject.
- ⑧ Conduct a urine pregnancy test in women of child-bearing potential. Do not conduct the test in case the subject had menopause, hysterectomy, bilateral oophorectomy, or bilateral salpingectomy.
- ⑨ Take a photograph of the target pressure ulcer.
- ⑩ Check the NPUAP Stage and size (using a scale) based on the pressure ulcer assessment and confirm whether the subject meets the inclusion criteria.
- ⑪ Review concomitant medication/treatment.

12.1.2 Visit 2 (enrollment, 1d)

Subject enrollment will take place at the second visit, and the following assessment will be conducted.

- ① Conduct the physical examination.
- ② Review the inclusion/exclusion criteria, and subjects who are finally determined eligible will go through the process of randomization.

- ③ Before applying the investigational device, check the infection signs using the CSSC(Clinical Signs and Symptoms Checklist).
- ④ Before applying the investigational device, take a photograph of the study ulcer, investigator will conduct a photo evaluation, and record the pressure ulcer size by a Scale.
- ⑤ After conducting standard dressing, apply the investigational device.
- ⑥ Record the baseline PUSH score.
- ⑦ Review concomitant medication and treatment-emergent adverse events.
- ⑧ Prescribe the investigational devices and train the subject or guardian on the self-dressing method.
- ⑨ Dispense the subject diary to record the frequency of position changes per day (if applicable) and the frequency of additional self-dressing.

12.1.3 Visit 3, 4, 5, 6, 7, 8, 9, 10, 11, 12, 13 (interim visit, 8d, 15d, 22d, 29d, 36d, 43d, 50d, 57d, 64d, 71d, 78d)

The following tests will be conducted at the interim visit. It can be replaced by home health care through coordinator's visit if the subject is not able to visit the institution.

- ① Conduct the physical examination.
- ② As vital signs, measure blood pressure, pulse, and body temperature.
- ③ Measure body weight (only 29d).
- ④ After removing the investigational device, take a photograph of the study ulcer, conduct the investigator's photo evaluation, and record the pressure ulcer size by a Scale and complete healing status.
- ⑤ Check the infection signs using the CSSC (Clinical Signs and Symptoms Checklist).
- ⑥ After conducting standard dressing, apply the investigational device.
- ⑦ After conducting the pressure ulcer assessment, record the PUSH score (15d, 29d, 43d, 57d, 71d).
- ⑧ Review concomitant medication and adverse events (all adverse events, local adverse events at the study ulcer).
- ⑨ Prescribe the investigational devices and train the subject or guardian on the self-dressing method.
- ⑩ At the last visit, investigational devices that have been prescribed but not used are to be returned.
- ⑪ Based on the subject diary, record the frequency of self-dressing beyond once-weekly in the Case Report Form.
- ⑫ Dispense the subject diary to record the frequency of position changes per day (if applicable) and the frequency of additional self-dressing.

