8.1 Inclusion criteria

- 1) Adults aged at least 19 years old as of the consent date
- 2) Pressure ulcer of the NPUAP (National Pressure Ulcer Advisory Panel) Stage III at screening
- 3) Pressure ulcer size of 3-100 cm² at screening
- 4) Written consent provided by the subject or representative
(In case a subject has more than one pressure ulcers that meet all inclusion criteria, the largest one is selected as a target lesion.)

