15.3 Analysis of efficacy endpoints

(1) Analysis of endpoints of main interest

- ① Number of patients with complete healing# of ulcer within 12 weeks
: Subjects who achieved complete healing and had early completion will be included.
- ② Time to complete healing# of ulcer within 12 weeks
: Time to complete healing is calculated as the number of days from baseline (1d).
(# The definition of complete healing: Epithelial tissue covering 100% of the study ulcer, no abrasion or ulceration, intact dermis and epidermis)
- ③ Pressure ulcer size reduction rate based on a scale at each time point

$$\text{Reduction rate} = \frac{\text{Pressure ulcer size on 1d}^* - \text{Pressure ulcer size at each time point from 8d to End-of-Study}^{**}}{\text{Pressure ulcer size on 1d}} \times 100\%$$

* Using a scale-based pressure ulcer area (cm²) measured prior to the study device application

** Using a scale-based pressure ulcer area (cm²) without re-epithelization*** measured at each time point after the study device application

(**Re-epithelization: New epithelial tissue covering the pressure ulcer, with no exudate, transudate, or avascular tissue)

- ① For subjects achieving complete healing within 12 weeks, present frequency and percentage.
 - ② For the time to 100% complete healing, analyze using the Kaplan-Meier method. Subjects not achieving 100% complete healing within 12 weeks will not be considered for evaluation for end point of main interest.
 - ③ For the pressure ulcer size reduction rate, present the mean and standard deviation.
- For the analysis for efficacy, conduct sub-analyses by use of local antibiotics and glucocorticoids for the pressure ulcer during the study.

(2) Analysis of other endpoints

- ① PUSH reduction rate at each time point

$$\text{Reduction rate} = \frac{\text{PUSH score on 1d} - \text{PUSH score at each time point}}{\text{PUSH score on 1d}} \times 100\%$$

- ② Dressing change frequency during the entire study period
: Calculated as the additional dressing frequency beyond twice weekly
- ③ Number of subjects with early completion due to complete healing during the study
- ④ Incidence of new infections at the pressure ulcer until Week 12 based on the CSSC

$$\text{Infection incidence} = \frac{\text{Number of subjects with at least 1 new infection** until Week 12, after the study device application}}{\text{Total number of subjects}} \times 100\%$$

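### Visit 2 lists randomisation ahead of the day 1 ulcer area, CSSC and PUSH, so in this open-label trial the baseline of several efficacy endpoints may be read with the arm known

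*Protocol*

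**What the plan says.** Protocol 12.1.2 numbers the Visit 2 activities:

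1. Physical examination.
2. Eligibility review and allocation: "Review the inclusion/exclusion criteria, and subjects who are finally determined eligible will go through the process of randomization".
3. CSSC infection signs, to be checked before the device goes on.
4. Baseline ulcer size, also before the device goes on: "take a photograph of the study ulcer, investigator will conduct a photo evaluation, and record the pressure ulcer size by a Scale".
5. Standard dressing, then device application.
6. Baseline PUSH score.

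The remaining items cover concomitant medication and adverse events, device prescription and training, and the diary.

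Protocol 12.2.4(2) repeats that the baseline ulcer assessment comes before the device. Protocol 15.3 defines the reference area of the size reduction rate as the one "measured prior to the study device application". None of these places ties the baseline to the moment when the allocation becomes known.

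Protocol 10.1 and SAP section 3 describe an open-label trial. Under Protocol 10.3 the investigator gives out the assigned number. Under 12.2.4 one investigator assesses a given subject throughout. No masked or independent photograph reader is named.

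**The concern.** A baseline value is protected by randomisation only if the arm cannot influence it. If the ruler, photograph and checklist are read after the assignment is known, a tendency to read larger or smaller in one arm enters the baseline, and random allocation cannot remove it because it arises afterwards.

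The day 1 values are used in four places:

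- **Size reduction rate** (Protocol 15.3, SAP 7.1): the 1d area is both the reference and the denominator. This is an endpoint of main interest.
- **Ulcer size change from 1d** (SAP section 8 and Table 0603): tested within group by a paired t-test.
- **PUSH reduction rate** (Protocol 15.3, SAP 7.1): the 1d score is both the reference and the denominator.
- **New infection** (Protocol 15.3, SAP 7.1): infection status at baseline decides which of two definitions applies to the subject.

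The SAP compares the arms on the two reduction rates by t-test and on new infections by Fisher's exact test. A baseline that differs by arm would feed those comparisons, with 10 subjects per group.

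**Working it through.** The plan states no figure to reproduce: 10 per group is given without a calculation. The first step compares passages. The rest is illustration, and the error sizes, standard deviations and test level in it are assumptions.

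**1. Order and safeguards.** The sections quoted above place allocation at item 2 and the baseline readings at items 3, 4 and 6. The timing rules in 12.1.2, 12.2.4 and 15.3 refer only to the device. A Visit 1 photograph and size exist before randomisation (12.1.1), but the Visit 1 size is not the denominator. Even when Visits 1 and 2 fall on one day, 12.1.1 lists as done once only the physical examination, the eligibility review and the concomitant medication review; ulcer size is not in that list.

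**2. Endpoints that do not use day 1 values.** Complete healing and time to healing do not use the baseline area. Vital-sign and laboratory changes are taken from Visit 1 (SAP Tables 0901 to 1004).

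**3. Effect on the size reduction rate.** Let R be the true reduction and e the relative over-reading of the 1d area. The recorded rate is 1 − (1 − R)/(1 + e), so the shift is (1 − R) × e/(1 + e).

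| True R | Recorded, e = 5% | Recorded, e = 10% |
|---|---|---|
| 0% | 1 − 1/1.05 = 4.8% | 1 − 1/1.10 = 9.1% |
| 50% | 1 − 0.5/1.05 = 52.4% | 1 − 0.5/1.10 = 54.5% |
| 80% | 1 − 0.2/1.05 = 81.0% | 1 − 0.2/1.10 = 81.8% |
| 100% | 100% | 100% |

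The example in Protocol 12.2.4 (5 cm² falling to 3.5, 2.2 and 0) gives 30.0%, 56.0% and 100%. With 5.5 cm² recorded on 1d it gives 36.4%, 60.0% and 100%.

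**4. How small a reading difference is enough.** Screening diameters are recorded to 0.1 cm. Adding 0.1 cm to both diameters of two of the protocol's example lesions gives:

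- 4.7 × 1.0 cm: (4.8 × 1.1)/4.7 = 5.28/4.70, or +12.3% in area.
- 2.0 × 1.5 cm: (2.1 × 1.6)/3.0 = 3.36/3.00, or +12.0%.

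On a 10 × 10 cm ulcer the same error is 10.1²/100, or +2.0%. The exposure is therefore mainly in small or narrow ulcers.

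**5. PUSH.** With a follow-up score of 5, a baseline of 10 gives (10 − 5)/10 = 50.0% and a baseline of 11 gives (11 − 5)/11 = 54.5%.

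**6. New infection.** Suppose two CSSC signs, neither of them purulent exudate, are present on 1d and persist. If both are recorded, the subject is infected at baseline and persistence is not a new infection. If only one is recorded, the subject is not infected at baseline, and two signs at the next visit count as new. One subject in a group of 10 is 1/10 = 10 percentage points.

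**7. Effect on a group comparison.** Assume a two-sided 5% t-test, 10 per group (18 degrees of freedom), no true difference, and a shift s in one arm only. The noncentrality is s/(SD × √(2/10)).

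| Shift s | SD 20 | SD 30 | SD 40 |
|---|---|---|---|
| 4.5 points | 7.6% | 6.2% | 5.7% |
| 9.1 points | 16.1% | 9.9% | 7.7% |

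The entries are false-positive rates against a nominal 5%.

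**8. Position of PUSH.** Protocol 12.2.11 has exudate estimated after the dressing is removed and before any topical agent is applied. Item 6 of 12.1.2 stands after device application. The two places must be reconciled.

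**The case against.** The strongest reply is that the order is inferred. Section 12.1.2 does not call its list a mandatory sequence or say when the assignment is disclosed. Items 3 and 4 carry their own timing words, which numbering alone would make unnecessary, and the place of PUSH suggests that the list is not strictly chronological. This stands in part. A reader might infer that the baseline is always taken with the arm known; the text supports only that it may be. But no section gives another order or a safeguard, so a site that follows the list as written reads the baseline after allocation.

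Other stronger readings go too far:

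- **Every change endpoint is affected.** Step 2 of the working shows otherwise.
- **The person who allocates also measures.** Protocol 10.3 has an independent statistician create and operate the list, and an investigator give the number; 12.2.4 fixes one assessor per subject. Neither says that these investigators are the same person. Under an open label the assessor can know the arm in any case.
- **The order defeats the aim of randomisation**, stated in 10.3 as "to reduce the possible bias which may be caused by the investigator". Allocation stays random; what is added is a possible measurement bias.
- **The size criterion should be applied again on 1d.** Protocol 8.1 sets "Pressure ulcer size of 3-100 cm² at screening", and a screening-based criterion is not an error. That is a separate choice about eligibility.

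It is also fair to say that photographs include a scale, use standardised settings and are kept as source documents, so a 1d reading could be checked against them and against Visit 1. That is true, but no such check is planned.

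Finally, the same open-label assessor reads the 12 later visits, so reordering protects one reading of 13. This stands as a limit on the benefit. The baseline reading, however, enters the reduction rate at every later visit at which ulcer remains.

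**Conclusion.** The point holds as a gap in the Visit 2 procedure: nothing requires the day 1 area, CSSC and PUSH to be recorded before the allocation is disclosed, and the list as written places them after it. The exposure is limited to the four baseline-dependent efficacy quantities named under the concern.

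The documents give no evidence that any bias would occur, or in which direction. If the 1d area were over-read by 5% to 10% in one arm, an unchanged ulcer in that arm would show a reduction of about 5% to 9%, a true 50% reduction would show as 52.4% to 54.5%, and a fully healed ulcer would be unaffected. The false-positive rates also rest on assumed SDs of 20 to 40 points and an assumed 5% level, since the plan states neither. They matter only if the SAP's tests are run; Protocol 16.2 says that there will be no formal test.

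The effect is modest, but it is avoidable at almost no cost. The change should be made.

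**What to change.** Reorder Protocol 12.1.2 as follows:

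1. Physical examination and eligibility review.
2. Day 1 photograph, ulcer area, CSSC and PUSH, all completed and recorded in the CRF.
3. Disclosure of the randomisation assignment.
4. Standard dressing and device application.

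Add one sentence to 12.2.4(2) stating that the baseline assessment is recorded before the assignment is disclosed, as well as before the device is applied. Placing PUSH in step 2 also reconciles it with the exudate direction in 12.2.11.

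The cost is an edit to one visit list, one added sentence, and a site instruction not to open the next assignment until the baseline entries are made. All the assessments already take place that day, and the target stays at 20 subjects. The eligibility criteria do not change.

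State the limit in the protocol: follow-up readings remain open-label, so this closes only the baseline route of bias.
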